1.3.1.3.2. Rat stroke

The ability of [¹¹C]PBR28 PET to localize TSPO in a rat permanent middle cerebral artery occlusion (MCAO) model of neuroinflammation was determined. [¹¹C]PBR28 was intravenously administered to rats at 4 and 7 days after permanent MCAO. In all experiments,

CONFIDENTIAL

This material is the property of Columbia University Medical Center. Do not disclose or use except as authorized in writing by the study sponsor

arterial blood was sampled for compartmental modeling of regional distribution volumes, and rat brains were sampled after imaging for *in vitro* [³H]PK 11195 autoradiography and histological evaluation. [¹¹C]PBR28 PET and [³H]PK 11195 autoradiography showed similar areas of increased TSPO, especially in the peri-ischemic core. Results from these *in vivo* and *in vitro* methods were strongly correlated.

1.4 Clinical Data to Date

1.4.1. Human experience with PBR28

[name] has 8 years experience using ¹¹C-PBR28 in clinical studies at the National Institute of Mental Health Intramural Research Program. Over 100 subjects received injection of ¹¹C-PBR28 in clinical protocols on which he was either PI or sub-Investigator. No AEs related to PBR28 administration have been reported.

1.4.1.1. Whole body studies

Whole-body images were acquired after intravenous bolus administration of ¹¹C-PBR28 in 7 healthy humans (651 +/- 111 MBq). For typical subjects, the 3 organs with highest exposure were those with the high TSPO densities (kidneys, spleen, and lungs), and the effective dose was 6.6 microSv/MBq[36].

1.4.1.2. Brain studies in controls

Results from the first *in-human* brain study of ¹¹C-PBR28 are as follows: Twelve healthy volunteers (1 female and 11 males, 25 ± 5 years of age, 81 ± 15 kg body weight) underwent brain imaging with ¹¹C-PBR28 with arterial catheterization[37]. Injected activity was 650 ± 92 MBq (17.6 ± 2.5 mCi). After injection of ¹¹C-PBR28, 10 of 12 subjects showed moderate levels of activity in brain that washed out gradually. The peak uptake occurred at 5 min and was ~ 200% SUV. Brain activity decreased to 50% of the peak by 70 min and to 40% of peak by 120 min. As expected from known distribution of TSPO in human brain, the distribution of activity was widespread and fairly uniform in gray matter of cerebral cortices and cerebellum, basal ganglia, and thalamus. The unconstrained two-tissue compartment model provided significantly better fit than the one-tissue compartment model, consistent with the presence of significant amounts of both specific and nonspecific binding in human brain.

These unusual subjects were initially referred to as “non-binders,” reflecting the apparently lack of interaction between ¹¹C-PBR28 and the target protein. In vitro binding assays using peripheral leukocytes isolated from blood samples taken from non-binders showed that these subjects expressed TSPO with ~50-fold lower affinity for ¹¹C-PBR28 than binders[38]. Later binding studies showed that there exist three patterns of ¹¹C-PBR28 binding in human subjects[39, 40]. High affinity binders (HABs) behave as though they express only TSPO that binds with high affinity, low affinity binders (LABs) behave as though they express only TSPO that binds with low affinity, and mixed affinity binders (MABs) behave as though they express both a high- and low-affinity version of TSPO. Genetic studies determined there is a strong association between TSPO binding status and the rs6971 (Ala147Thr) single nucleotide polymorphism on the TSPO gene[29]. HABs lack this polymorphism, LABs are homozygous, and MABs are heterozygous. As the allelic frequency of the polymorphism is 30% based on population studies, 9% are expected to be LABs. Caucasians and African Americans have highest prevalence of the polymorphism while it is rare in Han Chinese and Japanese. Our ex vivo study showed that statistical correction for TSPO genotype improves the ability of ³H-PBR28 to detect differences in TSPO density between controls and patients with schizophrenia in the dorsolateral prefrontal cortex[27]. Therefore, clinical studies have since employed the strategy of excluding LABs and performing statistical correction to remove the effect of systematic physiological differences in ¹¹C-PBR28 binding between HABs and MABs.

1.4.1.4. ¹¹C-PBR28 in Alzheimer’s disease

In our first AD PET study using ¹¹C-PBR28, we found that AD patients had greater binding than MCI patients or controls[41]. The largest differences were seen in parietal and temporal regions. ¹¹C-PBR28 binding correlated with clinical severity, brain atrophy, and earlier age of symptom onset. ¹¹C-PBR28 binding did not conclusively correlate with amyloid burden as measured with ¹¹C-Pittsburgh Compound B. This study used arterial blood sampling to calculate total distribution volume using the two-tissue compartment model, with correction for free fraction of radioligand. Even after TSPO genotype correction, variance of the PET data was relatively large (coefficient of variance = 34 - 73%).

We later used a simplified ratio method to measure ¹¹C-PBR28 binding in a larger sample (25 AD patients, 11 MCI patients, and 21 controls)[42]. By defining ¹¹C-PBR28 binding as uptake in a target region divided by that in cerebellum (standardized uptake value ratio, SUVR), we were able to detect differences between AD patients and controls in more regions with larger effect sizes. Variance of the PET data was much lower. Cerebellum was chosen because it is a large brain region relatively spared in AD (particularly early in disease). This simplified ratio method removes the need for arterial sampling and reduces the amount of time needed on the PET scanner.

1.5 Dose Rationale and Risk/Benefits

Based on prior human experience and human dosimetry data, we expect the proposed injected activity of ^{11}C -PBR28 (up to 20 mCi) to be safe without expected toxicity.

2 Study Objectives

Primary objectives

- 1). Determine feasibility of performing ^{11}C -PBR28 PET in patients with DLBD.
- 2). Determine effect size of ^{11}C -PBR28 binding in patients with DLBD vs. controls.

Our hypothesis is that ^{11}C -PBR28 binding will be greater in DLBD patients than controls, with largest differences in temporal and limbic regions.

Secondary objectives

- 1). Identify potential reference regions for ^{11}C -PBR28 binding in patients with DLBD.

Our hypothesis is that correcting cortical ^{11}C -PBR28 binding to that in the cerebellum, a region typically spared from pathology early in DLBD, will reduce intra-subject variance, avoid need for arterial catheterization, and improve sensitivity for detecting differences between DLBD patients and controls. We will also explore other potential reference regions such as cortical white matter.

- 2). Determine if ^{11}C -PBR28 binding correlates with cognitive impairment and Parkinsonism in patients with DLBD.

We postulate that ^{11}C -PBR28 binding will correlate with clinical severity (cognitive impairment and Parkinsonism) and the amount of atrophy on MRI.

3 Study Design

3.1 General Design

Subject selection. Patients and controls will be recruited from the ADRC, CUMC clinics, and direct referrals. Target accrual is $n = 4$ completers in each group (DLBD and controls). ADRC subjects who have already undergone GBA and ApoE genotyping through ADRC participation will be preferentially enrolled. If possible, only previously-determined GBA mutation carriers will be included. However, if not enough GBA mutation carriers are recruited to meet target enrollment we will also enroll GBA non-carriers who are also known ApoE4 noncarriers. This strategy is designed to reduce the inclusion of patients with co-existent AD-related tangle pathology, as GBA mutation and ApoE4 non-carrier status are both associated with pure DLBD pathology[14-16]. If we are still unable to meet target enrollment then we will include patients of unknown GBA and ApoE genotype. However, these patients will have ApoE genotyping performed in this study, and we will perform post-hoc analysis to see if ApoE4 status affects ^{11}C -PBR28 binding. ApoE testing will be done for research purposes only and results will not be disclosed to subjects. Subjects must have capacity to provide informed consent and consent will be obtained prior to study procedures.

CONFIDENTIAL

This material is the property of Columbia University Medical Center. Do not disclose or use except as authorized in writing by the study sponsor

Screening procedures. Subjects will undergo screening including history, physical examination, routine laboratory studies, neurological examination and brain MRI. Patients meeting clinical criteria for either dementia with Lewy bodies or Parkinson's disease dementia (collectively considered as DLBD) will be included. Diagnosis will be made via consensus conference using clinical criteria[42]. Screening will also include genetic analysis to exclude subjects homozygous for the rs6971 (Ala147Thr) SNP on the TSPO gene. Homozygous subjects have negligible binding on ^{11}C -PBR28 PET imaging and must be excluded; however, heterozygotes may be included[27, 41]. Clinical evaluation will include Montreal Cognitive Assessment (MoCA), Clinical Dementia Rating scale – sum of boxes (CDR-SB), and Unified Parkinson's Disease Rating Scale (UPDRS).

PET imaging procedures. Subjects will undergo ^{11}C -PBR28 PET in the CUMC Kreitchman PET center on a Siemens Biograph mCT. Prior to PET imaging, one arterial catheter and one intravenous catheter will be placed. After a low-dose CT scan for attenuation correction, up to 20 mCi ^{11}C -PBR28 will be injected intravenously over 60 seconds. Emission scan will begin at the start of the radioligand infusion according to the following frame schedule: 30 seconds x 6, 1 minute x 3, 2 minutes x 2, and 5 minutes x 16 for total scan time of 90 min. During the emission scan, arterial samples will be drawn at 10 second intervals for the first 4 min using an automated blood sampler. Thereafter, manual arterial samples will be drawn at 6, 8, 10, 15, 20, 30, 40, 50, 60, 75, and 90 minutes. Radioactivity in plasma will be quantified by a γ -counter and analyzed by reverse-phase chromatography to separate parent radioligand from radiometabolites[43] by the PET center radiometabolite laboratory. Free fraction of ^{11}C -PBR28 in plasma (f_p) will be measured by ultrafiltration and normalized using a standard derived from pooled donor plasma[44].

Image analysis. PET images will be analyzed using two methods. First, kinetic analysis will be performed using PMOD software (PMOD Technologies). Subject MR images will be coregistered to native space PET images and then segmented to define gray matter regions of interest (ROIs): prefrontal cortex, combined superior and inferior parietal lobule, occipital cortex, inferior temporal cortex, combined middle and superior temporal cortex, hippocampus, parahippocampal gyrus, anterior cingulate, amygdala, insula, and cerebellum. These regions have been selected based on where the largest number of Lewy bodies have been previously reported[45]. The two-tissue kinetic model using time-activity curves from each ROI and the metabolite-corrected arterial input function will be used to calculate total distribution volume, corrected for free fraction of radioligand in plasma (V_T/f_p). Second, the cerebellum will be used as a pseudo-reference region to calculate standardized uptake value ratios (SUVR) for each target ROI. To determine the best time interval for non-invasive measurement of TSPO binding in DLBD, we will calculate SUVR using different time intervals and compute correlation coefficients with the gold-standard measurement V_T/f_p . The time intervals that correspond to SUVR values that have strongest correlation with V_T/f_p will be used to calculate SUVR for the group comparisons between patients with DLBD and controls.

Statistical analysis.

Primary outcome

PET images will be analyzed using 1) the two-tissue kinetic model to calculate total distribution volume, corrected for free fraction of radioligand in plasma (V_T/f_p), and 2) the cerebellum as a pseudo-reference region to calculate standardized uptake value ratios (SUVR). Effect size will be

calculated for different regions as the difference in means (DLBD vs. controls) divided by the standard deviation.

Secondary outcomes

Coefficient of variation (%COV = standard deviation / mean) will be calculated for controls and patients with DLBD for both V_T/f_P and SUVR data. SUVR values will be calculated using cerebellum as reference regions. Additional reference regions will be explored. Correlation coefficients will be computed to look for correlation between ^{11}C -PBR28 binding (V_T/f_P and SUVR) and clinical severity. Severity will be measured using CDR-sum of boxes, MoCA score, and UPDRS. We will also look for correlations between ^{11}C -PBR28 binding and atrophy, as determined using ROI volumes derived from MRI data.

3.2 Primary Study Endpoints

Because the drug used in this study is a radioligand given at tracer doses, there are no clinical endpoints of the study.

The primary outcome measures are ^{11}C -PBR28 binding (using both V_T/f_P and SUVR). We expect binding will be greater in DLBD patients than in controls, with greatest difference in occipital, temporal, and parietal regions. We expect that ^{11}C -PBR28 binding in cerebellum will not differ between DLBD patients and controls and that this region can be used as a pseudo-reference region for non-invasive measurement of TSPO binding in DLBD. If we find that ^{11}C -PBR28 binding is different between patients and controls, we will explore other possible methods of non-invasive measurement. These methods include a cluster-based approach[46] or use of other potential pseudo-reference regions, such as white matter or whole gray matter.

3.3 Secondary Study Endpoints

N/A

3.4 Primary Safety Endpoints

N/A

4 Subject Selection and Withdrawal

4.1 Inclusion Criteria

Inclusion criteria for patients:

1. Age 60 and older
2. Meet criteria for either a) dementia with Lewy bodies, or b) Parkinson's disease dementia
3. Able to provide informed consent
4. Written and oral fluency in English

CONFIDENTIAL

This material is the property of Columbia University Medical Center. Do not disclose or use except as authorized in writing by the study sponsor

5. Able to participate in all scheduled evaluations and to complete all required tests and procedures.
6. In the opinion of the investigator, the subject must be considered likely to comply with the study protocol and to have a high probability of completing the study.

Inclusion criteria for controls:

1. Age 60 and older
2. Normal cognitive and motor function based on neurological examination
3. Written and oral fluency in English
4. Able to participate in all scheduled evaluations and to complete all required tests and procedures.
5. In the opinion of the investigator, the subject must be considered likely to comply with the study protocol and to have a high probability of completing the study.

Non-English speaking subjects will be excluded. The rationale is that because of the small scope of the study, we expect to reach accrual target with English speakers only. Also, because of the small scope we may not have resources for providing Spanish-speaking staff at all study visits.

4.2 Exclusion Criteria

1. Past or present history of certain brain disorders (other than DLB or PDD in the case of patient participants).
2. Certain significant medical conditions, which make study procedures of the current study unsafe. Such serious medical conditions include uncontrolled epilepsy and multiple serious injuries.
3. Contraindication to MRI scanning
4. Conditions precluding entry into the scanners (e.g. morbid obesity, claustrophobia, etc.).
5. Exposure to research related radiation in the past year that, when combined with this study, would place subjects above the allowable limits.
6. Low affinity binding on TSPO genetic screen
7. Currently taking anticoagulant drugs (e.g., warfarin)
8. Women who are able to become pregnant

4.3 Subject Recruitment and Screening

Patients and controls will be recruited from the ADRC, CUMC clinics, and direct referrals. Approximately 50% of enrolled subjects are expected to fail screening procedures or withdraw from the study. We therefore plan to screen 8 subjects in each group to ensure at least 4 in each group complete study procedures. Screening will also include genetic analysis to exclude subjects homozygous for the rs6971 (Ala147Thr) single nucleotide polymorphism on the TSPO gene.

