Objectives	
The primary objective is to generate pilot data in patients with DLBD. The aims are:
 
1. Determine feasibility of performing ¹¹C-PBR28 PET in patients with DLBD.2. Determine effect size of ¹¹C-PBR28 binding in patients with DLBD vs. controls. The exploratory aims are: 
1. Identify potential reference regions for ¹¹C-PBR28 binding in patients with DLBD.2. Determine if ¹¹C-PBR28 binding correlates with cognitive impairment and Parkinsonism in patients with DLBD.
Number of Subjects	
Target enrollment is 8 patients and 8 controls.
 
Target accrual is 4 patients and 4 controls.

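### Section 4.3: at the protocol's own 50% loss, screening 8 per group gives 4 completers on average and does not ensure at least 4

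*Combined protocol and SAP*

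**What the plan says.** Section 4.3 (Subject Recruitment and Screening) gives the loss: "Approximately 50% of enrolled subjects are expected to fail screening procedures or withdraw from the study". The next sentence draws the screening number from it: "We therefore plan to screen 8 subjects in each group to ensure at least 4 in each group complete study procedures".

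The Study Summary, under Number of Subjects, repeats both figures: "Target enrollment is 8 patients and 8 controls", and "Target accrual is 4 patients and 4 controls". Section 3.1 makes clear that accrual is counted in subjects who complete, four in each group.

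No section says what happens if a group has fewer than four completers after eight have been screened. Section 4.4 covers withdrawal and the use of data collected before it, but not replacement.

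**The concern.** The number 8 is the target divided by the expected yield, with no margin. A number chosen this way hits the target on average and falls below it a good part of the time. Section 4.3 nevertheless presents it as securing a minimum in each group, and it is the only means the plan names for doing so.

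Feasibility is the first primary objective, so the expected yield from screening ought to be described correctly. The second primary objective, the effect size, and the per-group coefficients of variation are calculated from the completers and are meant to inform a larger grant application. Section 4.1 also relies partly on the expectation of reaching the accrual target when it justifies enrolling English speakers only.

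**Working it through.** **Inputs.** Target of 4 completers per group (Study Summary; Section 3.1). Loss of about 50%, so completion probability p = 0.5 (Section 4.3). Number screened n = 8 per group (Section 4.3; Study Summary). Section 1.4.1.3 says that "9% are expected to be LABs"; low-affinity binders are excluded at screening, and I take this 9% as part of the 50%.

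**Reproducing the plan's figure.** n = 4 / (1 − 0.5) = 8. This matches. The expected number of completers is 8 × 0.5 = 4.

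**Chance of at least 4 completers if exactly 8 are screened.** With X ~ Binomial(8, 0.5):

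- P(X ≥ 4) = (70 + 56 + 28 + 8 + 1) / 256 = 163/256 = 0.637 for one group.
- Both groups: 0.637² = 0.405.
- At least one group short: 1 − 0.405 = 0.595.

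**Sensitivity to the loss rate**, since the 50% is approximate (8 screened per group, same loss in both):

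| Loss | One group reaches 4 | Both groups reach 4 |
|---|---|---|
| 40% | 0.826 | 0.683 |
| 45% | 0.740 | 0.547 |
| 50% | 0.637 | 0.405 |
| 55% | 0.523 | 0.274 |
| 60% | 0.406 | 0.165 |

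The protocol states the 50% for enrolled subjects overall, not by group. If, as an illustration, it were 60% in one group and 40% in the other, the chance for both would be 0.406 × 0.826 = 0.335. For 8 per group to give 90% for both groups, loss would have to be about 29% or lower.

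**Size of the shortfall.** P(X ≤ 3) = (1 + 8 + 28 + 56) / 256 = 93/256 = 0.363. Of these shortfalls, 56/93 = 60% are groups with exactly 3 completers. Both groups have at least 3 with probability (219/256)² = 0.73.

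**How many screens give real assurance at 50% loss.** For both groups to reach 4: 12 per group gives 0.859, 13 gives 0.910 and 15 gives 0.965.

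**If screening continued until 4 complete.** The expected number screened is 4 / 0.5 = 8 per group, so the planned figure would stand as a mean. A group would need more than 8 screens with probability 0.363, and more than 12 with probability 1 − 0.927 = 0.073.

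**The case against.** The strongest reply is that 8 is not a cap. Section 4.3 calls it a plan, the Study Summary calls it a target, and accrual is defined by completers. The site could simply screen a ninth subject. This stands: a reader might infer that screening stops at 8 and that the study will more likely than not (about 59%) miss its target, but no section says that screening stops there. What remains is that the documents do not say it may continue either, and the number 8 alone cannot secure the stated minimum.

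A second reply is that this is not a calculation error. That is also right. The quotient is correct; the fault lies in the claim attached to it and in the missing rule for a shortfall.

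A third is that falling to 3 matters little. A reader might infer that the effect size needs 4 completers per group and fails below that. The documents do not say so: 4 is a target with no precision argument behind it, and the Study Summary disclaims power to see significant group differences. With the approximation 1/√(2·df), the relative error of a single-group SD is about 41% with 4 subjects (3 df) and 50% with 3 (2 df). For a pooled SD it is about 29% with 4 + 4 (6 df) and 32% with 4 + 3 (5 df). The imprecision comes mainly from the target of 4 itself. A shortfall would also be a feasibility result in its own right.

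It might also be said that Section 4.4.2 lets data from withdrawn subjects be analysed where possible. That helps only for those who leave after a usable scan. It does nothing for screen failures and does not turn withdrawn subjects into completers.

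**Conclusion.** The claim in Section 4.3 does not follow from its own inputs: at about 50% loss, 8 screened per group gives 4 completers on average, not as a minimum. If 8 is the limit, the chance of at least 4 is about 64% in a given group and 41% in both, and for both groups it runs from 68% at 40% loss to 16% at 60% loss. These figures assume independent subjects and groups and the same loss in each group, none of which the documents state.

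The finding goes no further than that. It concerns a statement about accrual and an unstated rule for continuing. It does not show that the study will fall short, and it does not undermine the effect-size aim. It is cheap to correct and worth correcting.

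**What to change.** Choose one of the following.

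**(a) Keep 8 as the number screened per group and correct the claim.** In Section 4.3, replace the wording about ensuring at least 4 with: *expecting on average 4 completers per group (about a 64% chance of at least 4 in a given group and 41% in both)*. State the assumptions of independence and equal 50% loss beside the figures. The cost is a less favourable stated figure.

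**(b) Define the end of screening by completers.** In Section 4.3 and in the synopsis entry on numbers of subjects, state that screening in each group continues until 4 subjects complete, and that 8 is the expected number screened and not the limit. The cost is possibly a few extra screens, and no completers beyond 4 per group. With 8 screened regardless, (56 + 28 + 8 + 1) / 256 = 36% of groups would have 5 or more, and that possible gain is given up.

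The two should not be combined. Under (b), 64% and 41% are only the chances of reaching 4 within the first 8 screens, so quoting them as the chance of reaching 4 would put a wrong probability into the protocol.
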